10. ADVERSE EVENTS

Investigators who are is clinically qualified at consultant level will be responsible for the detection and documentation of events meeting the criteria and definitions detailed below.

There are likely to be adverse and severe adverse events including death, in patients with sepsis, as described in Appendix 3. The Chief Investigator and the clinical team will make decisions as to whether any such events are unexpected in terms of timing or severity and considered related to the study drug, with advice from the DMC as necessary.

The only expected adverse event as a result of the IMP is drowsiness manifesting as a decrease in sedation requirements as determined using the RASS score [24,25].

10.1 DEFINITIONS

ICU or HDU admission is a pre-requisite for study participation. AEs and SAEs as will be recorded and reported to the Sponsor within the specified time period as appropriate.

An **adverse event** (AE) is any untoward medical event affecting a clinical trial participant. Each initial AE will be considered for severity, causality or expectedness and may be reclassified as a serious event or reaction based on prevailing circumstances.

An **adverse reaction** (AR) is where it is suspected that an AE has been caused by a reaction to the trial drug

A serious adverse event (SAE), serious adverse reaction (SAR) or suspected unexpected serious adverse reaction (SUSAR) is any AE, AR or UAR that at any dose:

- results in death;
- is life threatening (i.e. the subject was at risk of death at the time of the event; it does not refer to an event which hypothetically might have caused death if it were more severe);
- requires hospitalisation or prolongation of existing hospitalisation;
- results in persistent or significant disability or incapacity;
- is a congenital anomaly or birth defect.

10.2 DETECTING AEs AND SAEs

All AEs and SAEs will be recorded from the time of study entry until the end of the study visit, defined as 24h for Stage 1 and up to 5 days for Stage 2 whilst patients remain on the ICU/HDU.

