4. STUDY POPULATION

4.1 NUMBER OF PARTICIPANTS

The study will be in two stages:

Stage 1: The first sequential cohort of 5 patients will be assigned to a single oral dose of 50mg melatonin given in a liquid formulation via nasogastric tube or orally as a drink if patients can tolerate this. Usual medical care will be at the discretion of the clinical treating team. Blood samples (10ml) will be obtained prior to melatonin adminstration, after 10 and 30 mins, and 1, 2, 6, 12 and 24h. A second cohort of 5 patients will receive 20mg melatonin and blood will be taken as above.

Once Stage 1 is complete and a dose and dosing interval decision has been made, a substantial amendment will be submitted to update the study protocol accordingly, prior to moving to Stage 2.

Stage 2: In stage 2, 40 patients will be randomised to receive either melatonin or placebo. The dose (20mg) and dosing interval (8 hourly) of melatonin will be based on data from Stage 1. The dose will be based on the maxmimum tolerated dose of melatonin at which first pass metabolism to 6-hydroxmelatonin is complete (20mg). The study will be conducted in a double blind fashion. Melatonin or placebo will be adminstered for 72h or until discharge from ICU or HDU if discharged before 72h. Usual medical care will be at the discretion of the clinical treating team. Subjects will be followed up daily whilst on the ICU/HDU for 5 days then mortality status at 28d will be recorded from medical records.

We propose a 72h dosing period for these reasons: 1. The median length of stay of patients on the ICU in Aberdeen is 4 days. This means that patients will either die or get better in this time frame. 2. Melatonin has been given in other disease conditions for much longer periods even at higher doses with no ill effects. 3. Many previous anti-inflammatory trials in this group of patients have administered trial medication for 72h.

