10.7 FOLLOW UP PROCEDURES

After initially recording an AE or recording and reporting an SAE, the Investigator will follow each participant as per the current SOP. As detailed in the protocol, AEs and SAEs will be followed up whilst the patient remains on ICU, for a maximum of 24h for Stage 1 and 5d for Stage 2. SUSARs will be followed up until resolution as per the SOP.

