APPENDIX 2:

Melatonin and Placebo oral liquid (see IMP Dossier for full details)

Table 1 Composition of Melatonin Oral Solution

Amount (mg/mL)	Reference to Standard	Function	Amount (mg/mL)
Melatonin	1	Internal monographs for pharmaceutical raw ingredients	Active ingredient
Methyl parahydroxybenzoate	1	Ph.Eur	Preservative
Potassium sorbate	1	Ph.Eur	Preservative
Glycerol (85 per cent)	100	Ph.Eur	Solubilizing agent
Hydrochloric acid (5M)	q.s. (~ 0.7 mg/mL)	Ph.Eur	pH-adjustment
Water purified	Ad 1 mL	Ph.Eur	Solvent

The Placebo will be identical but without melatonin.

Appendix 3

Expected events in patients with sepsis

System	Expected events	
Cardiovascular	Arrhythmia, hypotension, cardiac arrest, requirement for vasoactive drugs	
Respiratory	Respiratory failure, need for re-intubation	
Nervous	Confusion/delirium, neuro/myopathy	
Gastro-intestinal	GI/hepatic failure, bleeding, diarrhoea	
Renal	Oliguria, renal failure, requirement for RRT	
General	Readmission to ICU/admission from HDU to ICU,	
	digital ischaemia/necrosis	

RRT= renal replacement therapy

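### Stage 2 AE/SAE recording ends on leaving ICU/HDU, so safety observation time depends on a post-randomisation outcome and can stop within hours of the last dose

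*Protocol*

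**What the plan says.** Section 10.2 records all AEs and SAEs from study entry up to a cut-off that it gives as "defined as 24h for Stage 1 and up to 5 days for Stage 2 whilst patients remain on the ICU/HDU". Section 10.7 deals with follow-up of events already recorded: "AEs and SAEs will be followed up whilst the patient remains on ICU", to a maximum of 24h in Stage 1 and 5 days in Stage 2. It names ICU only. It makes one exception: "SUSARs will be followed up until resolution as per the SOP".

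Section 4.1 describes Stage 2 follow-up: "Subjects will be followed up daily whilst on the ICU/HDU for 5 days then mortality status at 28d will be recorded from medical records". Sections 4.1 and 6.3 give trial drug 8-hourly for up to 72h and stop it at ICU/HDU discharge if that comes sooner. Sections 2.2 and 7.2 also record length of stay and unit mortality.

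Appendix 3 lists events expected in patients with sepsis, among them "Readmission to ICU/admission from HDU to ICU". Nothing in the protocol extends AE/SAE recording to the ward or restarts it on readmission.

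**The concern.** The window closes at discharge or death. Both happen after randomisation and both reflect how the patient is doing. Length of ICU stay is itself recorded among the secondary outcomes, so the protocol allows that it may differ by arm. If it does, one arm is watched for longer than the other and raw AE counts are not like for like. Blinding does not correct this.

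The second problem needs no difference between arms. For an early-discharged patient, drug and recording stop together, so little time is left to see a delayed reaction. Section 1.1 reports that in healthy subjects the active metabolite was still raised 6h after a dose and back to baseline at 24h. A patient who relapses on the ward and returns to ICU has an event of a kind that Appendix 3 anticipates, but Section 10.2 has stopped recording by then.

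This matters because tolerability in sepsis is a stated aim (end of Section 1.1), and the draft DMC charter (Appendix 5) notes that high repeated doses are new in these patients. The safety data will inform a larger trial.

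**Working it through.** The protocol states no figure for observation time, so there is none to reproduce. The first step follows from the text. The others are illustrations.

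**1. Recording time after the last dose**

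Inputs: 8-hourly dosing, three times daily for up to 3 days (Section 6.3), and a 5-day cap (Section 10.2). Assume doses on schedule from time 0, so that nine doses run from 0h to 64h.

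- Discharged before 72h: the last dose was less than 8h before leaving, so post-dose recording is under 8h. Discharge at 25h, after the 24h dose, leaves 25 − 24 = 1h.
- Still on the unit at day 5: 120 − 64 = 56h.

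**2. Share leaving before day 5**

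Input: "The median length of stay of patients on the ICU in Aberdeen is 4 days" (Section 4.1). This is a figure for the ICU as a whole. Combined ICU/HDU stay is not given. If 4 days did apply, at least half of patients would leave before day 5 under any distribution.

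- Exponential stay: 1 − 2^(−5/4) = 0.58. Before 72h: 1 − 2^(−3/4) = 0.41.
- Lognormal with log-SD 0.6 or 1.0: 0.65 or 0.59 before day 5, and 0.32 or 0.39 before 72h.
- Varying the median, which matters more: for a median of 3 days, Φ(ln(5/3)/0.6) = 0.80. For a median of 8 days, Φ(ln(5/8)/0.6) = 0.22.

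Of 40 patients, 22% is about 9, 58% about 23 and 80% about 32. All these shares count deaths as exits.

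**3. Mean recorded time**

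This is the integral of the stay survival function S(t) from 0 to 5 days. For an exponential stay with median m it is (1 − 2^(−5/m)) × m/ln 2.

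- m = 4: 0.580 × 5.771 = 3.34 days. The two lognormal cases give 3.50 and 3.74, so the range is 3.3 to 3.7 of a possible 5 days.

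**4. What a difference in stay would do to counts**

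Assume an exponential stay, the same constant daily AE hazard in both arms, and no true safety difference.

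| Median stay, placebo v melatonin | Mean recorded days | Count ratio, melatonin/placebo |
|---|---|---|
| 4 v 3 days | 3.34 v 2.96 | 0.89 |
| 4 v 5 days | 3.34 v 3.61 | 1.08 |
| 4 v 6 days | 3.34 v 3.80 | 1.14 |

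With 20 per arm and an assumed hazard of 0.1 per day, 4 v 3 days gives 20 × 0.1 × 3.34 = 6.7 and 20 × 0.1 × 2.96 = 5.9 expected events. The difference is 0.8. The Poisson standard deviation of that difference is √(6.7 + 5.9) = 3.5.

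**5. Which moves fall outside the window**

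| Event within 5 days | Covered by Section 10.2? |
|---|---|
| HDU to ICU | Yes |
| ICU to HDU and back to ICU | Yes |
| Event on the ward after step-down | No |
| Readmission to ICU from a ward or home | No |
| Death after discharge | Not as an SAE, but captured in 28-day status |

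**The case against.** The best case on the other side is that this is a bounded choice in a 40-patient exploratory pilot. AE counts by arm are not a named Stage 2 endpoint. Deaths to day 28 are known for everyone, and SUSARs already detected are followed to resolution. Step 4 shows that sampling error would swamp the bias from a one-day shift in median stay. A drug that did harm by prolonging stay would be watched for longer, so more of its events would be recorded. Exposure-adjusted reporting can sit in an analysis plan that is not shown here.

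Most of that stands and limits the size of the point. It does not supply events that were never recorded: no analysis can recover a ward event, and the short post-dose observation exists whatever the effect on stay.

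A reader might go further in four ways that the documents do not support.

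- **That ICU readmission cannot be captured, so Appendix 3 contradicts Section 10.2.** Moves between HDU and ICU stay inside the window, and only readmission from a ward or home is lost. Appendix 3 supports judgements of expectedness. It is not a list of outcomes to collect.
- **That Section 10.7 deliberately narrows the window to ICU.** It concerns follow-up, not detection, and the protocol uses ICU loosely for ICU/HDU elsewhere (Section 6.3, for instance). This is probably loose wording, though it needs reconciling.
- **That the DMC's reviews are biased.** Section 12.3 says the DMC receives blinded data unless it asks otherwise. The draft charter does foresee closed-session safety data by group, so unequal windows could reach the DMC, but that is not established.
- **That more than half of patients will have a shortened window.** This rests on an all-ICU median, ignores HDU time and counts deaths.

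**Conclusion.** The point holds as a worthwhile, inexpensive improvement. The protocol itself fixes a Stage 2 safety window whose length depends on a post-randomisation outcome, and it leaves early-discharged patients with hours of post-dose recording. Both follow from Sections 4.1, 6.3 and 10.2 without any modelling beyond doses being given on schedule. Ward events and readmission from a ward are not recorded as AEs or SAEs.

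The comparison between arms is weakened only if melatonin changes length of stay. The direction is then unknown and the likely size modest: count ratios of about 0.89 to 1.14 for the shifts tried, assuming exponential stay and equal daily hazard. The number of patients affected is uncertain, roughly 22% to 80% leaving before day 5 for medians of 8 to 3 days, deaths included. Stage 1, with its nominal 24h window, is little affected.

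**What to change.** - In Sections 10.2 and 10.7, record AEs and SAEs from study entry to a fixed 5 days after first dose for every surviving Stage 2 patient regardless of ward, using hospital notes after step-down.
- Reconcile ICU in Section 10.7 with ICU/HDU in Section 10.2.
- Note any ICU readmission at the 28-day records check already planned in Section 4.1, since a 5-day window would still miss later ones.
- Report events by arm over that common window.

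The cost is protocol and CRF wording plus a brief notes review for patients discharged alive before day 5. Section 10.3 already has investigators consult hospital notes when documenting events. No dose or treatment rule changes.

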10.3 RECORDING AEs AND SAEs

Depending on severity, when an AE/SAE occurs, the Investigator will review any documentation (e.g. hospital notes, laboratory and diagnostic reports) related to the event and record all relevant information in the CRF and on the AE or SAE form.

Information to be collected will include dose of any medication, type of event, onset date, Investigator assessment of severity and causality, date of resolution as well as treatment required, investigations needed and outcome.

10.4 EVALUATION OF AEs AND SAEs

Seriousness, causality, severity and expectedness will be evaluated. Please also refer to Appendix 3.

10.4.1 Assessment of Seriousness

The Investigators will make an assessment of seriousness as defined in Section 10.1 and whether any events are usual and expected and/or considered related to the study drug, with advice from the DMC as necessary. Please also refer to Appendix 3.

10.4.2 Assessment of Causality

The Investigator will make an assessment of whether the AE/SAE is likely to be related to treatment according to the following definitions:

Unrelated: where an event is not considered to be related to the study drug.

Possibly: although a relationship to the study drug cannot be completely ruled out, the nature of the event, the underlying disease, concomitant medication or temporal relationship make other explanations possible.

Probably: the temporal relationship and absence of a more likely explanation suggest the event could be related to the study drug.

Definitely: The known effects of the study drug or its therapeutic class, or based on challenge testing, suggest that study drug is the most likely cause.

All AEs/SAEs judged as having a reasonable suspected causal relationship (e.g. possibly, probably, definitely) to the study drug will be considered as ARs/SARs. All AEs/SAEs judged as being related (e.g. possibly, probably, definitely) to an interaction between the study drug and another drug will also be considered to be AR/SAR.

Alternative causes such as natural history of the underlying disease and other risk factors and the temporal relationship of the event to the treatment in these critically ill patients will be considered. Please also refer to Appendix 3.

10.4.3 Assessment of Severity

The Investigators will make an assessment of severity for each AE/SAE and record this on the CRF according to one of the following categories:

Mild: an event that is easily tolerated by the participant, causing minimal discomfort and not interfering with every day activities.

Moderate: an event that is sufficiently discomforting to interfere with normal everyday activities.

Severe: an event that prevents normal everyday activities.

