4.2 INCLUSION CRITERIA (for both Stage 1 and Stage 2)

Adult patients (16 years or over) on the ICU or HDU at Aberdeen Royal Infirmary with sepsis due to community acquired pneumonia who are within 24h of fulfilling the criteria for sepsis with clinical suspicion of pneumonia and the presence of chest X-ray changes consistent with pneumonia will be recruited. The criteria for sepsis are:

- clinical suspicion or evidence of acute infection
- systemic inflammatory response syndrome, defined by two or more of the following:
 - 1. Core temperature <36°C or >38°C;
 - 2. tachycardia: heart rate > 90 beats/min;
 - 3. tachypnoea: respiratory rate > 20 breaths/min or ventilated;
 - 4. leucocyte count >12 x 10^{9} /L or <4 x 10^{9} /L.

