12.3 DATA MONITORING COMMITTEE

An independent Data Monitoring Committee (DMC) will be established to oversee the safety of subjects in the trial and will comprise of 3 consultants in intensive care who are external to Aberdeen . The terms of reference of the DMC and the names and contact details of the Chair are detailed in Appendix 5. The DMC will be provided with data after Stage 1 and after each 10 patients are randomised to Stage 2. The data provided will be blinded. No data will be unblinded (unless requested for safety concerns), until the end of the study, unless emergency unblinding is required. The DMC will agree terms of reference and other procedures prior to the study starting. The DMC will monitor the trial data in 'virtual' meetings after Stage 1 and after every 10 patients randomised to

Stage 2 and be regularly provided with all relevant data. The DMC will make recommendations as to any modifications that are required to be made to the protocol and advise on study termination if they are of the opinion the severity of unexpected adverse events in the study population is unacceptable. If the DMC has safety concerns and request data to be unblinded, a third party will oversee unblinding.

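### Adverse-event severity is graded by effect on everyday activities, which separates events poorly in ICU/HDU patients, although severity feeds expectedness decisions and the DMC's termination advice

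*Protocol*

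**What the plan says.** Section 10.4.3 applies one three-level scale to all events: "The Investigators will make an assessment of severity for each AE/SAE and record this on the CRF". The lowest level joins discomfort to activities: "Mild: an event that is easily tolerated by the participant, causing minimal discomfort and not interfering with every day activities". The middle level joins the same two elements at a higher degree: "Moderate: an event that is sufficiently discomforting to interfere with normal everyday activities". The highest level drops discomfort and uses activities only: "Severe: an event that prevents normal everyday activities".

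Section 10.1 fixes the setting: "ICU or HDU admission is a pre-requisite for study participation". Section 10.2 limits recording to the study visit, "defined as 24h for Stage 1 and up to 5 days for Stage 2 whilst patients remain on the ICU/HDU".

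Severity is then relied on in two places. Section 12.3 has the DMC "advise on study termination if they are of the opinion the severity of unexpected adverse events in the study population is unacceptable". The opening of section 10 has the Chief Investigator and clinical team decide whether events of the kind listed in Appendix 3 are unexpected, with timing and severity as the criteria. Neither place refers to the 10.4.3 grades, and the protocol defines severity nowhere else.

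**The concern.** The anchors presuppose a person whose daily routine an event can disturb. Here the routine has been disturbed before the event occurs, by sepsis and by admission to a critical care unit. An assessor who follows the wording has no clear way to separate a small event from a large one.

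Two uses are at stake. First, Appendix 3 lists events such as hypotension, arrhythmia and renal failure as expected, without a grade. Under section 10, only timing or severity can make a listed event unexpected. Expectedness in turn bears on SUSAR classification (10.4.4) and expedited reporting (10.6). Second, severity of unexpected events is the only ground for DMC termination advice in the body of the protocol. The draft charter notes that high repeated doses have not been given to patients with sepsis before, so an informative safety record is a main product of this pilot.

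**Working it through.** The plan gives no figure to reproduce and no arithmetic decides the point. The check sets the sections beside each other and applies the scale as written.

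**Inputs**

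- Scale: 10.4.3, as quoted above.
- Setting and recording window: 10.1 and 10.2, so every graded event falls within the ICU/HDU stay.
- Patients' condition: section 4.2 accepts "respiratory rate > 20 breaths/min or ventilated" as one of the inflammatory-response criteria. Section 5.2 expects consent to come more often from a legal representative than from the patient. Sections 1.2 and 10 monitor sedation with RASS.
- Planned participants: 5 + 5 = 10 in Stage 1 and 40 in Stage 2, so 10 + 40 = 50.

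**Step 1: can the activity anchor be rated?** Take two Appendix 3 events of very different weight, diarrhoea and cardiac arrest, in a ventilated patient. The wording allows three readings.

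| Reading of the anchor | Diarrhoea | Cardiac arrest |
|---|---|---|
| The patient's state during the event | Severe, because activities are already prevented | Severe, for the same reason |
| The further loss of activities caused by the event | No further loss, so mild at most | No further loss, yet clearly not mild, so no grade fits |
| The loss the event would cause in someone otherwise well | The assessor's guess | Severe, by supposition |

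The first reading puts both events in one grade. The second leaves the graver event without a grade. The third separates them, but only through a hypothetical that the protocol does not describe and that assessors may apply differently.

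**Step 2: does discomfort rescue the scale?** It can help for awake patients and for the two lower grades. It cannot help with the top grade, which does not mention it, or with patients who cannot report how they feel. The one reaction that section 10 expects from the drug, drowsiness seen as a lower sedation requirement, shows the difficulty: in a sedated patient neither anchor describes it.

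**Step 3: does seriousness substitute?** Section 10.1 defines seriousness without reference to daily activities, so it is unaffected. But it does not rank non-serious events, and it does not show whether an expected event was worse than usual, which is what section 10 asks.

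**Step 4: is better information already collected?** Yes. Section 10.3 records the treatment required, the investigations needed and the outcome of each event. The material for a usable grade is on the form, but the grade does not draw on it.

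**The case against.** The strongest reply is that nothing decisive hangs on the grade. Section 12.3 asks for the opinion of a committee that it describes as intensive care consultants, and it cites neither 10.4.3 nor a threshold. The protocol also uses the word severe loosely, in places where serious seems meant. Expedited reporting follows seriousness, causality and expectedness. This stands in part: the link from the grade to the DMC is inferred. But 10.4.3 holds the only definition of severity. If 12.3 and section 10 mean something else, their criterion is undefined. Either way the text needs an addition.

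A reader might infer four stronger things that the documents do not support.

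- *The scale collapses to a single grade because no such patient has everyday activities.* The protocol does not say this. HDU patients are eligible, some may drink the dose or consent for themselves, and the lower grades also use discomfort.
- *The DMC cannot recognise harm.* The draft charter (Appendix 5) has it monitor toxicity, serious events and deaths. It provides for safety data by treatment group in closed sessions and lists harm, benefit, futility and external evidence among possible reasons for early stopping.
- *Termination advice rests on the grade alone.* The charter's wider grounds rule this out.
- *A severity table by arm would be uninterpretable.* The protocol promises no such table.

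A further objection concerns the remedy. Appendix 3 already expects vasoactive drugs, re-intubation and renal replacement, so grades based on intervention could crowd at the top. A life-threatening anchor would also duplicate a seriousness criterion. Both points are fair, and both shape the fix.

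**Conclusion.** The point holds as a defect in the wording of 10.4.3. The anchors suit people going about their lives, and they separate events poorly in patients whose activities are already limited by illness and admission. Its reach is every graded event in 50 planned participants. Its effect on the distribution of grades cannot be quantified, because the protocol does not give the proportion ventilated, sedated or able to report symptoms.

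The conclusion rests on two assumptions. The first is that critical illness and ICU/HDU care restrict ordinary activities, which is a safe inference but is not stated. The second is that severity in section 10 and in 12.3 is meant to be the severity defined in 10.4.3, which the text leaves open. Safety oversight does not fail if the wording stays, because other safety data reach the DMC. This is a worthwhile and inexpensive improvement.

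**What to change.** - Replace the 10.4.3 anchors with ones that can be rated against the patient's state just before the event, using what 10.3 already records. For example: lowest grade, no change in care; middle grade, added monitoring or non-urgent intervention; top grade, urgent intervention or new or increased organ support relative to that baseline. These words classify events after they occur and set no treatment rule.
- Do not use life-threatening as a severity anchor, so that severity stays distinct from the seriousness criteria in 10.1.
- State in the opening of section 10 and in 12.3 that this scale is the severity measure meant, and align the draft charter with it.

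The cost is a few lines of protocol text submitted under section 14.1, a change to the AE form and brief retraining of assessors. Events already graded on the present wording could be regraded from the 10.3 fields.
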